We could demonstrate a significantly improved reperfusion by 38% after 20 minutes ischemia in the skeletal muscle 24 hours after heme arginate administration in a sample size of 12 healthy subjects⁶. We used this data concerning the skeletal muscle for the sample size calculation of this trial. For a desired alpha of 0.05 and a power of 80%, the calculated sample size is 8. However, myocardial tissue may react in a different way to heme arginate administration. Therefore, the randomizer program will be programmed to distribute the first 24 patients evenly in all three groups. An intermediate evaluation of the outcome parameters will be performed by ANOVA (applying the Bonferroni correction). We hypothesize that the sample size of 12 patients per group for this trial may be appropriate. If the intermediate evaluation provides significant results to answer the study endpoints, no additional subjects will be included. If not, a sample size calculation will be performed based on the results of the first 24 patients. If more than 36 patients are required to answer the proposed questions, an amendment will be formulated to the ethical board and the competent authority.

Safety and tolerability endpoints

The treatment-emergent AEs will be tabulated (if possible, coded by using the MedDRA dictionary. Adverse events leading to premature discontinuation of study drug will be listed and summarized similarly to AEs. Treatment-emergent SAEs will be listed and summarized similarly to AEs, separately for treatment-emergent SAEs and SAEs occurring before study drug initiation and after study drug discontinuation. Reasons for premature discontinuation of study drug will be listed and summarized by frequency.

Vital signs (blood pressure and pulse rate) will be summarized for the absolute values and for the change from baseline to each scheduled time point of measurement. Individual subject listings will be provided.

Baseline parameters and concomitant medications

Continuous demographic variables (age, height, weight, BMI) will be summarized by the usual location and scale statistics (mean, median, standard deviation, minimum, maximum and number of available observations).

Qualitative demographic characteristics (race) will be summarized by counts and percentages. Other subject characteristics (medical history, physical examination findings, previous and concomitant medications) will only be listed.

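### After a failed look the sample size is recalculated from that look's own results, with no HO-1 difference, comparison, alpha or power fixed in advance; if the observed effect is the input, the answer tends to exceed the planned 36

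*Combined protocol and SAP*

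**What the plan says.** All of this stands in the combined protocol and SAP, under Statistical methodology and analysis, Sample size considerations.

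- The starting calculation uses a result in skeletal muscle of healthy subjects, a "significantly improved reperfusion by 38% after 20 minutes ischemia in the skeletal muscle 24 hours after heme arginate administration". From it: "For a desired alpha of 0.05 and a power of 80%, the calculated sample size is 8".
- The section accepts that myocardium may respond differently. It therefore has the randomisation program "distribute the first 24 patients evenly in all three groups", which is 8 per group.
- At that point: "An intermediate evaluation of the outcome parameters will be performed by ANOVA (applying the Bonferroni correction"). The number of comparisons or endpoints behind the correction is not given.
- After success: "If the intermediate evaluation provides significant results to answer the study endpoints, no additional subjects will be included". After failure: "If not, a sample size calculation will be performed based on the results of the first 24 patients".
- On the final size: "We hypothesize that the sample size of 12 patients per group for this trial may be appropriate". This agrees with the 36 patients under Investigational plan, Design. Beyond that: "If more than 36 patients are required to answer the proposed questions, an amendment will be formulated".

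No HO-1 difference, fold change or SD is stated anywhere. Outcome Variables lists several main outcomes: mRNA and protein, in heart and in blood cells, plus dose-response. None is named as the one that drives the recalculation.

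**The concern.** The recalculation is reached only when the result at 8 per group was not significant, and it then uses that same result. With no HO-1 difference set in advance, the natural input is the difference just observed. That difference has been selected for being small, so on average it understates the true effect.

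An observed effect that just misses significance at 8 per group has roughly 50% power there. Sizing for 80% power on it asks for many more patients. A trial for which 12 per group is enough could then be told that it needs far more. Each added patient has two right-ventricular biopsies (Description of study days). Because comparison, alpha and power are also open, the size could be settled by choices made with the data in view.

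**Working it through.** **Inputs.** From the plan: alpha 0.05, power 80%, 8 per group at the look, 12 per group planned, ANOVA with Bonferroni. Assumed, because not stated: two-sided tests, normal data with equal SDs, a Bonferroni divisor of 3 (all pairs of three groups), 80% power in the recalculation, and the true effects used in step 4.

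**1. The plan's own 8.** It cannot be reproduced, because no SD is given. Inverting n = 2(z_α + z_β)²/d² with 1.960 + 0.842 = 2.802 gives d = 2.802 × √(2/8) = 1.40 (1.51 by exact t). For a 38-point effect that means an SD of 38/1.40 = 27 or 38/1.51 = 25. So 8 per group is attainable, but for muscle reperfusion, not HO-1.

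**2. Can a failed look return 12 per group?** Find the observed d for which the formula gives 12, convert it to t at 8 per group (t = d/√(2/8) = 2d), and compare with the critical value at the look.

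- Sizing at 0.05: d = 2.802 × √(2/12) = 1.144, so t = 2.29. The critical value at 0.05 is 2.08 (pooled SD, 21 df) or 2.14 (two-group SD, 14 df). A t of 2.29 is already significant, so a failed look cannot return 36.
- Sizing at 0.05/3: d = (2.394 + 0.842) × √(2/12) = 1.321, so t = 2.64. The critical value at 0.05/3 is 2.60 (21 df): again already significant. On 14 df it is 2.72, so 36 can just be reached.
- Look at 0.05/3, sizing at 0.05: any t from 2.29 to 2.60 is non-significant and still returns 36 or fewer.

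**3. Smallest total after a failed look**, with d at the boundary, t_crit × √(2/8):

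| Look / sizing alpha | SD | Boundary d | Normal formula | Exact t |
|---|---|---|---|---|
| 0.05 / 0.05 | pooled | 1.040 | 45 | 48 |
| 0.05 / 0.05 | two-group | 1.072 | 42 | 45 |
| 0.05/3 / 0.05/3 | pooled | 1.301 | 39 | 42 |
| 0.05/3 / 0.05/3 | two-group | 1.359 | 36 | 39 |
| 0.05/3 / 0.05 | pooled | 1.301 | 30 | 30 to 33 |

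Example, first row: 2 × 2.802²/1.040² = 14.5, so 15 per group and 45 in total.

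**4. Typical totals after a failed look.** Simulation of 400,000 looks for one active-versus-placebo comparison, 8 per group, pooled SD on 21 df, observed effect put into the normal formula. A true effect of 1.18 SD is what 12 per group detects with 80% power at 0.05. An effect of 1.5 SD is close to what the stated 8 implies.

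| True effect | Look / sizing alpha | Look fails | Returns 36 or fewer | Median total |
|---|---|---|---|---|
| 1.18 | 0.05 / 0.05 | 38.5% | 0% | 87 |
| 1.18 | 0.05/3 / 0.05/3 | 57.8% | 0% | 78 |
| 1.18 | 0.05/3 / 0.05 | 57.8% | 20% | 60 |
| 1.5 | 0.05 / 0.05 | 18.5% | 0% | 72 |
| 1.5 | 0.05/3 / 0.05/3 | 34.5% | 0% | 63 |
| 1.5 | 0.05/3 / 0.05 | 34.5% | 30% | 48 |

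The selection bias is plain: with a true effect of 1.18 SD, the mean observed effect among looks that fail at 0.05 is 0.68 SD.

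**5. SD-only alternative.** Keep the difference at its preset value (1.18 true SDs), size at 0.05 and re-estimate only the SD. The median after a failed look is then 12 to 13 per group.

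**The case against.** The strongest reply is that the plan never says the observed difference will be used. Basing a calculation on the first 24 patients' results is equally compatible with re-estimating only the SD. If d = 1.40 were kept as the planned effect and sized at 0.05, that would return 36 or fewer in 93% of trials when the SD is as planned, and in 59% when it is 1.2 times as large (not conditioned on the look). This stands, and it is why the point is conditional. Yet SD-only re-estimation needs a preset HO-1 difference, and the plan has none.

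A reader might infer that 36 can never come out of the rule. The documents do not support that:

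- The plan applies Bonferroni at the look, and 0.05 is the only alpha it states for sizing. Combining the two allows 36 or fewer.
- A two-group SD at 0.05/3 reaches exactly 36 by the normal formula. Larger divisors, plausible with several main outcomes, can reach it too: a divisor of 6 at both steps gives 33 to 39.
- If both active-versus-placebo tests must succeed but the larger difference drives the sizing, 36 or fewer is common (59 to 73% at 1.5 SD).
- On the omnibus F at 0.05 (critical value 3.467), f² = 2 × 3.467/24 = 0.289 gives 39, but f² = 2 × 3.467/21 = 0.330 gives 33.

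A reader might also infer that the rule typically doubles the trial, or that nothing controls its size. The first depends on an assumed true effect, and the documents give none for HO-1. The second overlooks that going above 36 requires an amendment to the ethics committee and the competent authority.

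**Conclusion.** The concern holds conditionally. The recalculation is triggered by failure and fed by the failed data, with its effect, comparison, alpha and power left open. If the observed effect is used, it is biased low. If one alpha serves both steps (0.05, or 0.05/3 with the pooled SD), a non-significant pairwise result must ask for more than 36: at least 42 to 48, or 39 to 42, with medians of about 63 to 87 for true effects of 1.5 to 1.18 SD. With Bonferroni only at the look, 36 or fewer is possible but is the minority outcome for those effects, at about 20 to 30% (median 48 to 60).

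The medians rest on the assumed effects. The minima rest only on the testing assumptions listed in the working. The point does not invalidate the trial. It should be fixed because the remedy is a better method, not just more detail, and it is cheap.

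**What to change.** Replace the recalculation sentence with:

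> If not, the sample size is recalculated from the pooled within-group SD of log HO-1 in the first 24 patients and an HO-1 difference, comparison, alpha and power (80%) fixed before the look; the observed group difference is not used. If the result is 36 or fewer, the trial completes 36; if more, an amendment is sought.

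The protocol must also name which HO-1 measure (mRNA or protein, in which tissue) the calculation refers to. The alpha should be the one used in the final test. At 0.05/3, the SD-only calculation for a difference of 1.18 SD gives a median of 16 per group after a failed look, because 12 per group then has less than 80% power.

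Cost: protocol wording, and a choice in advance of one HO-1 fold change worth detecting. Downside: if the true effect is smaller than that, the trial may end at 36 without significance.

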In case of premature discontinuation after study drug intake, the subjects will be closely followed until dismissal. They may request that from the time point of withdrawal no more data will be recorded and that all biological samples collected in the course of the study will be destroyed.

Premature termination of the study

The sponsor has the right to close this study at any time. The IEC and the competent regulatory authority must be informed. The trial will be terminated prematurely in the following cases:

- If adverse events occur which are so serious that the risk-benefit ratio is not acceptable
- If the number of dropouts is so high that proper completion of the trial cannot realistically be expected

Safety definitions and reporting requirements

Averse events (AEs)

Summary of known and potential risks of the study drug

Heme arginate has been used in humans to treat acute episodes of hepatic porphyrias since 1985 and is well tolerated. The most commonly observed AEs of intravenous infusion of heme arginate are local reactions. Known AEs are listed in detail in Table 2.

Definition of adverse events

An AE is any adverse change from the subject's baseline condition, i.e., any unfavourable and unintended sign including an abnormal laboratory finding, symptom or disease that occurs during the course of the study, whether or not considered related to the study drug.

A treatment-emergent AE is any AE temporally associated with the use of a study drug, whether or not considered related to the study drug.

Adverse events include:

- Exacerbation of a pre-existing disease.
- Increase in frequency or intensity of a pre-existing episodic disease or medical condition.
- Disease or medical condition detected or diagnosed after study drug administration even though it may have been present prior to the start of the study.
- Continuous persistent disease or symptoms present at baseline that worsen following the start of the study.
- Lack of efficacy in the acute treatment of a life-threatening disease.
- Events considered by the investigator to be related to study-mandated procedures.
- Abnormal assessments, e.g., ECG and physical examination findings, must be reported as AEs if they represent a clinically significant finding that was not present at baseline or worsened during the course of the study.

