Hospitalization is defined as an overnight stay in a hospital unit and/or emergency room.

An additional overnight stay defines a prolongation of existing hospitalization.

The following is not considered an SAE and should be reported as an AE only:

- Treatment on an emergency or outsubject basis for an event not fulfilling the definition of seriousness given above and not resulting in hospitalization.

The following reasons for hospitalizations are not considered AEs, and therefore not SAEs:

- Hospitalizations for cosmetic elective surgery, social and/or convenience reasons.
- Standard monitoring of a pre-existing disease or medical condition that did not worsen, e.g., hospitalization for coronary angiography in a subject with stable angina pectoris.
- Elective treatment of a pre-existing disease or medical condition that did not worsen, e.g., hospitalization for chemotherapy for cancer, elective hip replacement for arthritis.

SAEs related to study-mandated procedures

Such SAEs are defined as SAEs that appear to have a reasonable possibility of causal relationship (i.e., a relationship cannot be ruled out) to study-mandated procedures (excluding administration of study drug) such as discontinuation of subject's previous treatment during a washout period, or complication of a mandated invasive procedure (e.g., blood sampling, heart catheterization), or car accident on the way to the hospital for a study visit, etc.

Suspected unexpected serious adverse reactions (SUSARs)

SUSARs are all suspected adverse reactions related to the study drug that are both unexpected (not previously described in the SmPC) and serious.

Severity of adverse events

The severity of clinical AEs is graded on a three-point scale: mild, moderate, severe, and reported on specific AE pages of the CRF.

If the severity of an AE worsens during study drug administration, only the worst intensity should be reported on the AE page. If the AE lessens in intensity, no change in the severity is required.

If an AE occurs during a washout or placebo run-in phase and afterwards worsens during the treatment phase, a new AE page must be filled in with the intensity observed during study drug administration.

Mild

Event may be noticeable to subject; does not influence daily activities; the AE resolves spontaneously or may require minimal therapeutic intervention;

Moderate

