Event may make subject uncomfortable; performance of daily activities may be influenced; intervention may be needed; the AE produces no sequelae.

Severe

Event may cause noticeable discomfort; usually interferes with daily activities; subject may not be able to continue in the study; the AE produces sequelae, which require prolonged therapeutic intervention.

A mild, moderate or severe AE may or may not be serious. These terms are used to describe the intensity of a specific event (as in mild, moderate, or severe myocardial infarction). However, a severe event may be of relatively minor medical significance (such as severe headache) and is not necessarily serious. For example, nausea lasting several hours may be rated as severe, but may not be clinically serious. Fever of 39°C that is not considered severe may become serious if it prolongs hospital

discharge by a day. Seriousness rather than severity serves as a guide for defining regulatory reporting obligations.

These definitions do not apply to clinically significant and asymptomatic laboratory test abnormalities or abnormal assessments (e.g., ECG findings) considered as AEs. The investigator should tick non-applicable on the AE page of the CRF to qualify the intensity of the AE.

Relationship to study drug

For all AEs, the investigator will assess the causal relationship between the study drug and the AE using his/her clinical expertise and judgment according to the following algorithm that best fits the circumstances of the AE:

Unrelated:

- May or may not follow a reasonable temporal sequence from administration of the study product
- Is biologically implausible and does not follow known response pattern to the suspect study drug (if response pattern is previously known)
- Can be explained by the known characteristics of the subject's clinical state or other modes of therapy administered to the subject.

Possibly related:

- Follows a reasonable temporal sequence from administration of the study product.
- May follow a known response pattern to the study drug (if response pattern is previously known).
- May also be reasonably explained by the subject's clinical state or other modes of therapy administered to the subject.

Probably related:

- Follows a reasonable temporal sequence from administration of the study drug.
- May follow a known response pattern to the study drug (if response pattern is previously known).

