- Could not be reasonably explained by the known characteristics of the subject's clinical state or other modes of therapy administered to the subject, if applicable.

Definitely related:

- Follows a reasonable temporal sequence from administration of the study drug.
- Follows a known response pattern to the study drug (if response pattern is previously known).
- No other reasonable cause is present.

Reporting procedures

A special section is designated to adverse events in the case report form. The following details must thereby be entered:

- Type of adverse event
- Start (date and time)
- End (date and time)
- Severity (mild, moderate, severe)
- Serious (no / yes)
- Unexpected (no / yes)
- Outcome (resolved, ongoing, ongoing – improved, ongoing – worsening)
- Relation to study drug (unrelated, possibly related, probably related, definitely related)

Adverse events are to be documented in the case report form in accordance with the above mentioned criteria.

Reporting procedures for SAEs

In the event of serious, the investigator has to use all supportive measures for best patient treatment. A written report is also to be prepared and made available to the clinical investigator within five days. The following details should at least be available:

- Patient initials and number
- Patient: date of birth, sex, ethical origin
- The suspected investigational medical product (IMP)
- The adverse event assessed as serious
- Short description of the event and outcome

Reporting procedures for SUSARs

It must be remembered that the regulatory authorities, and in case of SUSARs which could possibly concern the safety of the study participants, also the Institutional Review Board / Independent Ethics Committee (IRB / IEC) are to be informed. Such reports shall be made by the study management and the following details should be at least available:

- Patient initials and number
- Patient: date of birth, sex, ethical origin
- Name of investigator and investigating site
- Period of administration
- The suspected investigational medical product (IMP)
- The adverse event assessed as serious and unexpected, and for which there is a reasonable suspected causal relationship to the IMP
- Concomitant disease and medication
- Short description of the event (description, onset and (if applicable) end, therapeutic intervention, causal relationship, hospitalization or prolongation of hospitalization, death, life-threatening, persistent or significant disability or incapacity

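### The required adverse-event items have no code for death or sequelae and no item for relation to the study biopsies, and the severity grades contradict their own examples

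*Combined protocol and SAP*

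**What the plan says.** The Reporting procedures section introduces its list as mandatory: "A special section is designated to adverse events in the case report form. The following details must thereby be entered". Three items on that list matter here.

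- **Outcome:** "Outcome (resolved, ongoing, ongoing – improved, ongoing – worsening".
- **Causality:** "Relation to study drug (unrelated, possibly related, probably related, definitely related". No other causality item is listed.
- **Severity:** three grades, mild, moderate and severe.

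Other sections define what these items have to carry. Definition of adverse events counts as an adverse event "Events considered by the investigator to be related to study-mandated procedures". SAEs related to study-mandated procedures sets up a separate class, which leaves out administration of the drug: "Such SAEs are defined as SAEs that appear to have a reasonable possibility of causal relationship". It gives as an example a "complication of a mandated invasive procedure (e.g., blood sampling, heart catheterization". Description of study days mandates two right-ventricular biopsies during surgery, one before cross-clamping and one after protamine. The SAE section puts fatal events first among its criteria.

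Under Severity of adverse events, a moderate event is one without sequelae. For a severe event, "the AE produces sequelae, which require prolonged therapeutic intervention". The explanatory text that follows says that the grades describe intensity, mentions severe headache as an event of minor medical significance, and states that "nausea lasting several hours may be rated as severe". It also tells the investigator to mark severity as not applicable for clinically significant but asymptomatic laboratory or ECG findings.

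**The concern.** The protocol defines classes of event that its own data items cannot identify. The biopsies are done only for the study, and the Risk/Benefit assessment relies in part on their bleeding risk being very low. Placebo patients are biopsied too, so comparing arms cannot reveal biopsy harm. The investigator's attribution of each event is the only source, and no item asks for it. Such a judgement is easily made at the time of surgery and may not be recoverable later.

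The outcome list leaves no correct code for a patient who dies or who recovers with lasting damage. The severity text gives two incompatible rules, so two careful assessors could grade the same event differently.

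**Working it through.** No figure in the plan is at stake, so the check sets the texts side by side.

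**1. Outcome.** The four codes are resolved and three forms of ongoing. A fatal event is neither resolved nor ongoing. An event that ends with sequelae has to be entered as resolved, which hides the sequelae, or as ongoing, which misstates the course. There is no code for unknown.

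**2. Causality.** Take a bleed from a biopsy site. It is an adverse event under the definition quoted above, and if serious it belongs to the procedure-related class. The only causality question is about the drug. Under Relationship to study drug the most natural answer is unrelated, because the bleed has another explanation and does not follow the drug's known response pattern. Bleeding from the valve surgery itself gets the same answer, so the two share a code. The content listed under Reporting procedures for SAEs names the suspected medicinal product and a short description, with no procedure item. A non-serious event does not generate an SAE report at all. The number of biopsies that this item would cover is 2 × 36 = 72, or 2 × 24 = 48 if the trial stops at the intermediate evaluation.

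**3. Severity.** The other descriptors of moderate and severe are softened by words such as may or usually. The sequelae clauses are not, and they point in opposite directions, so they are what separates the two grades. Applied as written:

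- Several hours of nausea with full recovery leaves no sequelae and fails the severe definition, yet the explanatory text allows it to be severe.
- A life-threatening event with full recovery also fails the severe definition.
- An event with sequelae that need no prolonged treatment fits neither moderate nor severe.

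The severe grade therefore cannot stand in for a sequelae code either: an investigator who follows the examples will use it for events without sequelae.

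**4. Not applicable.** The severity text requires this option; the item list offers three grades only.

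**5. Effect on planned output.** Safety and tolerability endpoints plans a tabulation of treatment-emergent events, a summary of events leading to discontinuation, and listings and summaries of SAEs by period. None is specified by severity, outcome or cause, so the planned counts do not use the defective items.

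**Scale, for illustration only.** The documents give no operative mortality. With an assumed risk p per patient, the chance of at least one death among n patients is 1 − (1 − p)^n.

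- n = 36: 1 − 0.99^36 = 30% at p = 1%; 1 − 0.97^36 = 67% at p = 3%.
- n = 24: 1 − 0.99^24 = 21% at p = 1%; 1 − 0.97^24 = 52% at p = 3%.

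These are chances that a fatal code would be needed. They are not chances that a death would be lost.

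**The case against.** The strongest reply is that nothing important goes missing. A death is an SAE, is flagged as serious on the adverse-event page, has its outcome described in the SAE report, and appears in the SAE listing. A biopsy-site bleed can be named under type of event, which has no fixed codes. Seriousness, not severity, drives regulatory reporting, and life-threatening events are SAEs whatever their grade. The printed case report form is not among the documents and may hold more than the list; the reference to a not-applicable tick on the page hints at that.

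Much of this stands. A reader might infer that the trial could not record a death. The documents do not support that: only the coded outcome item lacks the value. A reader might also infer that the planned safety tables would misstate postoperative events. That does not follow, because those tables do not use outcome, severity or cause. Nor is any bias between arms shown, since all arms are biopsied. The early-termination ground refers to the seriousness of events and to risk-benefit; it mentions neither severity grades nor tables.

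The reply does not remove the gap. Free text under type of event is neither required to mention the biopsy nor coded, and the SAE narrative covers serious events only. If the printed form does hold more items, the protocol list should say so. The contradiction in the severity text remains whatever the form looks like.

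**Conclusion.** The point holds as a defect in the protocol's required adverse-event items and severity definitions. Deaths, sequelae and biopsy-related events could not be summarised from coded adverse-event data, and severity would be graded inconsistently because the definitions and the examples disagree. Main outcomes, planned event counts and SAE reporting are unaffected.

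The most consequential part is the missing biopsy attribution. It concerns up to 72 biopsies with no unbiopsied comparison group, and it may not be possible to reconstruct afterwards. The missing fatal code is a smaller matter because the SAE route captures deaths. The illustrative 30–67% for 36 patients rests wholly on an assumed mortality of 1–3%.

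The conclusion rests on two readings: that the list in Reporting procedures is what the form collects, and that the descriptors within a severity grade apply together. The change is worth making before enrolment because it is cheap and the attribution must be collected at the time.

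**What to change.** - **Outcome:** add *fatal*, *resolved with sequelae* and *unknown*.
- **Causality:** add a second item, *relation to study biopsy / other study procedure*, and add a table of it to Safety and tolerability endpoints.
- **Severity item:** add *not applicable*, to match the severity text.
- **Severity definitions:** remove the sequelae clauses from moderate and severe, so that sequelae are recorded under outcome and the grades agree with the stated examples of severe events.

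If the printed form already carries any of these, align the protocol list with it. The cost is a wording change to the protocol and form, one more item for the investigator per adverse event, and one extra table.
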